7. NOTATION OF TREATMENT GROUPS AND VISITS

Notation of treatment groups

The following notation of **treatment groups** will be used throughout the report:

Full Notation (as used in the study protocol)	Notation Used Throughout All Tables, Listings, and Figures
Tapinarof Cream 1%	Tapinarof Cream 1%
Vehicle	Vehicle Cream

Visit terminology

Visit	Notation Used Throughout All Tables, Listings, and Figures
Screening, Days -30 through Day -1, Visit V1	Screening
Baseline, Day 1, Visit V2	Baseline
Week 1, Day 8, Visit V3	Week 1
Week 2, Day 15, Visit V4	Week 2
Week 4, Day 29, Visit V5	Week 4
Week 8, Day 57, Visit V6 (End of Treatment)	Week 8
Week 9, Day 64, Visit V7 (End of Study/Follow-up) [1]	Week 9

Note: phone calls to assess AEs and concomitant medications, to review study drug application procedures, and to confirm subject's continued participation in the study will occur on Week 3 (Day 22) and Week 6 (Day 43).

[1] Subjects who choose not to participate in the OL-LTE study or who fail to qualify for participation in the OL-LTE study will complete a Follow-up Visit (Week 9 visit) approximately 1 week after the end of treatment in this study.

Analysis visits

Study days are measured from date of first dose of study medication. Study days corresponding to measurements are calculated as:

- Assessment date date of first dose + 1 if assessment date is on or after the date of first exposure of treatment.
- Assessment date date of first dose if assessment date is before the date of first exposure of treatment.

All efficacy and safety endpoints will be analyzed according to the nominal visits (i.e., actual visit) except for assessments collected on early termination and unscheduled visits. Early termination and unscheduled visits will be re-numbered to an analysis visit based on their windowed visits defined by actual study day. If more than one visit occurs within a single visit window, then the analysis will take the one closest to the target day. If the 2 visits are equidistant from the target day, the visit with later date and time will be used.

The following analysis visit windows will apply to early termination and unscheduled visits:

Analysis Visit	Target Day	Analysis Visit Window
Baseline	1	1
Week 1	8	Post first dose to Day 12
Week 2	15	Day 13 – Day 21
Week 4	29	Day 22 – Day 42
Week 8	57	Day 43 – Maximum (last day of treatment + 3 days, Day 59)
Week 9	64	>Maximum (last day of treatment + 3 days, Day 59)

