6.3.4 Clinical Safety Laboratory Assessments

All protocol-required laboratory assessments must be conducted in accordance with the Study Reference Manual or Laboratory Manual and the protocol Schedule of Assessments ([Table 1](#)). Laboratory requisition forms must be completed, and samples must be clearly labeled with the subject number, protocol number, site number, and visit date. Details for the preparation and shipment of samples will be provided by the laboratory and are detailed in the Study Reference Manual or the Laboratory Manual. Reference ranges for all safety parameters will be provided to the site by the laboratory responsible for the assessments.

A list of clinical laboratory tests and parameters is provided in [Table 4](#).

All laboratory tests with values that are considered clinically significantly abnormal during participation in the study should be repeated until the values return to normal or baseline. If such values do not return to normal within a period judged reasonable by the Investigator, the etiology should be identified, if possible, and the Sponsor and Medical Monitor notified.

Table 4: Laboratory Tests

Diagnostic Screening Tests		

• HBsAg• Hepatitis C antibody• Anti-HBc• Anti-HBs^a		

• Pregnancy tests: (serum at Screening and urine at other visits when performed; women of CBP only)^b• FSH (as needed in women of non-CBP only)• At the Investigator's discretion, subjects may be screened for alcohol and illicit drug use.		
Serum Chemistry		

• BUN• Creatinine• Glucose (fasting not required)• Sodium• Potassium• Chloride	
• Total carbon dioxide• Calcium• AST• ALT• Alkaline phosphatase	
• Uric acid• Total bilirubin (+fractionated if required)• Total protein• Albumin
Hematology		

• Platelet count• RBC count• WBC count (absolute)• Hemoglobin• Hematocrit	
• RBC Indices:
• MCV• MCH• MCHC• Reticulocyte percentage	
• WBC Differential:
• Neutrophils• Lymphocytes• Monocytes• Eosinophils• Basophils
Urinalysis		

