13.4 Clinical Laboratory Evaluation

Laboratory values will be classified as normal, low, or high based on normal ranges supplied by the laboratory. Changes from baseline in abnormality status will be summarized using shift tables by visit.

For quantitative laboratory measures, observed values and changes from baseline will be summarized descriptively by visit and treatment group.

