13.7 Electrocardiogram

The ECG data analysis will be conducted based on methodology recommended in the ICH E14 guideline (International Council for Harmonisation, 2005)⁹.

Overall interpretation results for ECG will be summarized using shift tables (Normal, Abnormal Not Clinically Significant, Abnormal Clinically Significant) comparing baseline to end of treatment (Week 8). Descriptive statistics at baseline and at each post-baseline time point as well as changes from baseline will be summarized for each ECG parameter.

In addition, a categorical summary of abnormal corrected QT interval (QTc) values will be presented. At each time point, the number of subjects with QTc according to Fridericia's formula, QTcF and QTc according to Bazett's formula (QTcB) values of >450 ms, >480 ms, and >500 ms will be presented. At each post-baseline time point, the number of subjects with change from baseline values in QTcF and QTcB of >30 ms and >60 ms will be presented.

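### With the scheduled visit attended, SAP 7 leaves most unscheduled and some early termination labs and ECGs out of the by-arm tables, and the visible SAP 13.4 and 13.7 plan no worst-value summary

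*SAP*

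**What the plan says.** SAP 7 (Analysis visits) opens with "All efficacy and safety endpoints will be analyzed according to the nominal visits" and makes an exception for early termination and unscheduled assessments: "Early termination and unscheduled visits will be re-numbered to an analysis visit based on their windowed visits defined by actual study day". It then adds "If more than one visit occurs within a single visit window, then the analysis will take the one closest to the target day", followed by "If the 2 visits are equidistant from the target day, the visit with later date and time will be used". The window table that follows is said to apply to early termination and unscheduled visits. No separate rule for safety data is given.

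SAP 13.4 states: "Changes from baseline in abnormality status will be summarized using shift tables by visit". Observed lab values and changes are also by visit. SAP 13.7 plans an ECG interpretation shift from baseline to Week 8, descriptive ECG statistics by time point, and QTc threshold counts at each time point. Neither section mentions a worst or any-post-baseline summary.

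Protocol 6.3.4 says that clinically significant abnormal labs "should be repeated until the values return to normal or baseline". Protocol 7.10 allows labs at unscheduled visits, and ECGs at subset sites, for AE follow-up among other reasons. Protocol 7.9 includes labs, and ECGs at subset sites, in the Early Termination Visit.

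**The concern.** Choosing the record nearest a target day suits an efficacy endpoint, where one value per visit is wanted. Safety tables also need to show whether a subject ever had an abnormal value. Under SAP 7, a lab or ECG taken between scheduled visits is usually not selected when the scheduled visit was attended, and the visible plan has no other by-arm table to pick it up. The same holds for some results taken at withdrawal, which can follow an AE. Listings keep the values but give no comparison between arms. For AEs, by contrast, SAP 13.2 does summarize the maximum grade per subject.

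A second issue is that SAP 7 does not say whether a nominal visit competes with a re-numbered one in the same window. If it does, a repeat lab can take the place of the abnormal scheduled value that prompted it.

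**Working it through.** The plan gives no figure to reproduce, so the check works through the rule day by day.

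**Inputs.**
- Targets and windows (SAP 7): Week 4 is Day 29, window Days 22-42. Week 8 is Day 57, window from Day 43 to the later of Day 59 and last treatment day + 3.
- Scheduled visits: Days 27-31 and Days 55-59 (Protocol 7.5 and 7.6, ±2 days).
- Labs and ECGs are scheduled after baseline at Weeks 4 and 8, not at Weeks 1 and 2 (Protocol 7.3 to 7.6).

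**Rule.** Distance = |study day − target day|. The smaller distance wins, and a tie goes to the later record. This takes the literal reading, in which nominal and re-numbered visits compete. Same-day pairs are left out.

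**Week 4.** The window has 21 days, so each scheduled day has 20 other days: 5 × 20 = 100 pairs.

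| Scheduled day | Unscheduled days that win | Days that lose (of 20) |
|---|---|---|
| 27 | 28-31 | 16 |
| 28 | 29, 30 | 18 |
| 29 | none | 20 |
| 30 | 29 | 19 |
| 31 | 28-30 | 17 |

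Losses: 16 + 18 + 20 + 19 + 17 = 90 of 100.

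**Week 8.** With the window taken as Days 43-59 (17 days), there are 5 × 16 = 80 pairs.

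| Scheduled day | Unscheduled days that win | Days that lose (of 16) |
|---|---|---|
| 55 | 56-59 | 12 |
| 56 | 57, 58 | 14 |
| 57 | none | 16 |
| 58 | 57 | 15 |
| 59 | 56-58 | 13 |

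Losses: 12 + 14 + 16 + 15 + 13 = 70 of 80. If the window runs past Day 59, the added days lie at least 3 days from target and also lose.

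**Other reading.** If nominal visits do not compete, the unscheduled record loses in all 100 and all 80 pairs. The literal reading is therefore the more favorable one for unscheduled values.

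**Early termination.** An in-window Week 4 visit is at most 2 days from target. A result on Days 32-42 is 3 to 13 days away, so it always loses. Taking Week 4 as scheduled on Day 29, terminations on Days 2-56 (55 days) divide as follows:
- Days 2-21 (20 days): mapped to Week 1 or 2, where no labs or ECGs are scheduled. The SAP does not say whether these values are tabulated.
- Days 22-29 (8 days): kept as Week 4.
- Days 30-42 (13 days): lost to Week 4.
- Days 43-56 (14 days): kept as Week 8.

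20 + 8 + 13 + 14 = 55.

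**Replacement, literal reading only.** A repeat on a later day displaces the scheduled value in these cases:
- Week 4 on Day 27, repeat on Days 28-31.
- Week 4 on Day 28, repeat on Days 29-30.
- Week 8 on Day 55, repeat on Days 56-59.
- Week 8 on Day 56, repeat on Days 57-58.

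If the scheduled visit is on or after the target day, no later-day repeat can displace it.

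**ECG interpretation shift.** An early termination ECG before Day 43 maps to Week 1, 2 or 4. A Baseline-to-Week-8 table cannot include it, whichever record wins its window.

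**The case against.** The strongest reply is that the values are not lost. SAP 6 puts all individual data in listings. Protocol 8.1.1 makes abnormal labs that the investigator judges clinically significant AEs, apart from those tied to the underlying disease, and SAP 13.2 summarizes treatment-emergent AEs by arm. Since Protocol 6.3.4 requires repeats only for clinically significant labs, most values in the replacement scenario should also appear as AEs. This stands and limits the consequence. AE capture still rests on investigator judgment and does not fill the lab shift or QTc tables.

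Second, SAP 7 can be read as leaving nominal visits outside the windows. Replacement then never occurs. That reading is reasonable, so replacement is a possibility and not a finding. The omission of unscheduled values remains, and becomes complete wherever a nominal value exists.

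Third, a reader might infer that the tables must look cleaner than the data. The documents do not show this. Unscheduled visits also cover drug dispensing and missed visits, early termination labs are routine for every withdrawal, and repeats taken until normal add normalized values that the rule often discards while keeping the abnormal scheduled one.

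Fourth, SAP Appendix C is not visible, so a worst-value table may already be planned there. If so, SAP 13 should say so.

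**Conclusion.** The point holds as a gap in the safety summaries. With the scheduled visit attended in window, the rule excludes an unscheduled lab or ECG in 90 of 100 day pairs at Week 4 and 70 of 80 at Week 8, and excludes every early termination result on Days 32-42. These shares give each day equal weight. They describe how the rule works and do not forecast how many values will be affected, which the documents do not allow anyone to derive.

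Four stronger inferences are not supported:
- That early termination results drop out in general. They are used when they are the only or closest record in their window, and from Day 43 they count as Week 8.
- That a normal repeat will replace an abnormal value. This needs the literal reading, an early in-window visit and a repeat within a few days (or a same-day repeat at a later time).
- That the window rule causes the ECG shift gap. It comes from the Week 8-only design in SAP 13.7. Earlier early termination ECGs can still enter the time-point summaries.
- That the planned 15% and 30% losses (267 × 0.15 and 133 × 0.30, about 40 subjects per arm) measure the ECGs omitted. Those are loss-to-follow-up assumptions, and such subjects would seldom have an early termination ECG. Neither dropout timing nor the size of the ECG subset is given.

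The change is worth making because it is cheap and uses data already collected.

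**What to change.** 1. In SAP 13.4, add a lab shift table from baseline to the worst post-baseline value over all scheduled, unscheduled and early termination records, with lowest and highest values handled separately.
2. In SAP 13.7, add QTc threshold counts (absolute and change from baseline) on the worst post-baseline value over the same records, and a baseline-to-worst post-baseline ECG interpretation shift.
3. In SAP 7, state that the nominal visit takes precedence in by-visit safety tables, with an unscheduled or early termination value used only when the nominal value is missing. This settles the ambiguity but does not close the gap by itself: without items 1 and 2 it would exclude every unscheduled value wherever a nominal one exists.

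The cost is SAP wording and a few table rows. Abnormality counts may be slightly higher, and worst-value counts depend partly on how often a subject is tested, which a footnote can say. The change should precede unblinding, because SAP 6 treats later additions as post hoc.

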8. ANALYSIS SETS

The safety population will be used for the safety analyses and will include all randomized subjects who receive at least 1 application of study drug. Treatment assignment will be based on the treatment received.

The following subject populations will be used for efficacy analyses:

- The intent-to-treat (ITT) population will include all randomized subjects. Treatment assignment will be based on the randomized treatment.
- The per-protocol (PP) population will exclude ITT subjects with protocol deviations or other events that may impact the interpretation of the primary efficacy endpoint, regardless of whether the deviation(s) is considered major or minor. Exclusion criteria for the Per-protocol population may include:
 - Failure to meet the enrollment inclusion/exclusion criteria
 - Specified use of prohibited concomitant medication

Systemic Agents:

- Oral/systemic corticosteroids for >5 days
- Oral PDE4 inhibitors used for atopic dermatitis (e.g., roflumilast, apremilast); or other conditions if not on stable dose for period prior to and over course of the study
- Any oral immunosuppressive medication including cyclosporine, Imuran (azathioprine), methotrexate, tacrolimus, any Janus kinase inhibitor
- Injected IL4/13 blocking biologic including lebrikizumab, dupilumab
- Oral/systemic retinoids (e.g., alitretinoin), if not on a stable dose for period prior to and over course of the study
- Other injected monoclonal antibodies with potential impact on AD (omalizumab)
- Oral/systemic antihistamines for ≥ 3 days when used for skin conditions
- Oral/systemic antibacterials for ≥ 3 days when used for skin conditions
- Other investigational drug

Topical Agents:

- Topical immunomodulators on affected skin (other than transient <5
 days focal treatment for AESI) including topical corticosteroids, topical
 calcineurin inhibitors (Elidel, Protopic), topical PDE4 inhibitor
 (crisaborole/Eucrisa), coal car containing products
- Topical emollients containing keratolytics (including salicylic acid, urea) on affected skin (other than transient ≤7 days focal treatment for AESI)
- Topical antihistamines for ≥ 3 days when used for skin conditions
- Topical antibacterials limited to gentamicin and neomycin
- Other investigational drug
- Failure to be compliant with treatment regimen (compliance < 80%)
- Inclusion of scalp in efficacy assessment (see protocol section 5.1.5)

Final determination of subject inclusion in the PP population will be made before unblinding. Treatment assignment will be based on the treatment received.

The PK population will be used for the PK analyses and will include all subjects who undergo plasma PK sampling and have evaluable concentration-time data for analysis. A sample that is below the quantification limit (BQL) of the assay is considered evaluable. Treatment assignment will be based on the treatment received.

9. STUDY POPULATION

9.1 Subject Disposition

Subject disposition information will be summarized for all subjects by treatment and overall. Summaries will include: the number of subjects screened, the number of enrolled (randomized) subjects, the number of subjects in each population, the number of subjects completing the treatment phase of the study, the number of subjects completing the study through follow-up and primary reason for discontinuation, and number of days in the study (defined as study completion/discontinuation date – treatment start date + 1).

In order to describe the impact of COVID-19 on current study, the following disposition events will be summarized in the tables separately:

- Subjects discontinued from the treatment/study as a result of a positive COVID-19 diagnosis.
- Subjects discontinued from the treatment/study due to other reasons related to COVID-19. This is excluding COVID-19 diagnosis but may include reasons such as site closure, travel restrictions, fear of infection, etc.
- Subjects with study visits altered (including modified in-clinic visit, virtual and phone visits) and missed due to COVID-19.

COVID-19 related protocol deviations will be summarized separately. The impact of COVID-19 (including protocol deviation, visit alteration, treatment/study discontinuation and diagnosis of COVID-19) will also be flagged at subject-level in a data listing. Subject profile will be used to compile all COVID-19 related information for affected subjects.

Also, all COVID-19 related symptoms and confirmed cases that occur during the study will be reported as AEs and included in the summaries.

9.2 Protocol Deviations

Major protocol deviations that could potentially affect the efficacy or safety conclusions of the study will be identified before database lock and unblinding of individual subject treatment information. Major protocol deviations may include, but are not limited to:

- Randomized subjects who did not satisfy selected inclusion and exclusion criteria;
- Subjects who received the wrong treatment or an incorrect dose;
- Subjects who received an excluded concomitant treatment;
- Failure to have a Week 8 assessment within ± 7 -day visit window;
- Non-compliance with the dosing regimen. A subject will be considered compliant with the dosing regimen if they applied ≥80% of the expected doses. Expected number of doses is based on length of time enrolled in the treatment-phase of the study.

Reasons for exclusion of a subject from the analysis and protocol violations (minor/major) will be listed.

All protocol deviations, including the deviation designation (major or minor), category, and indication of whether the deviation led to an exclusion of a subject from the PP population, will be presented in a data listing.

Protocol deviations will be summarized by deviation category and treatment group. In addition, COVID-19 related protocol deviations will be summarized separately.

9.3 Eligibility

Subjects not fulfilling any eligibility criteria will be presented in a data listing.

9.4 Demographic and Baseline Characteristics

Demographic variables include age, sex, ethnicity, race, and Fitzpatrick skin type. Age will be reported on the CRF and will be based on age at time of signing informed consent.

Other baseline characteristics include height, weight, body mass index (BMI), vIGA-ADTM, %BSA, EASI score, and PP-NRS.

Demographic and baseline characteristics will be summarized for the safety, ITT, and PP populations.

Medical history

The verbatim term of the medical history condition/event will be coded using the Medical Dictionary for Regulatory Activities (MedDRA), Version 24.0.

A summary table will be prepared by treatment and in total. The summary will show the system organ class (SOC) and preferred terms (PT) ordered by descending subject count in the total column by SOC and PT.

9.5 Prior and Concomitant Medications

Prior and concomitant medication verbatim terms in the eCRFs will be mapped to Anatomical/Therapeutic/Chemical (ATC) class and preferred names using the WHODrug global dictionary (Version B3 01MAR2021).

Prior (within the 30 days before screening, and with stop dates prior to first dose of study drug) and concomitant (ongoing or with stop dates on or after first dose of study drug) medications will be listed by subject for each treatment group. If the medication is ongoing or the stop year is missing, the medication will be considered as received for the entire duration of the study.

To distinguish prior vs concomitant medications, the following rules for stop dates will apply:

• If only year was recorded, and it is before Baseline, it is a prior medication; if year is same or after Baseline, it is assumed to be a concomitant medication.

- If day is missing, but month and year are before Baseline, it is a prior medication; if month and year are the same as Baseline, it is assumed to be a concomitant medication; if month and year are after Baseline, it is a concomitant medication.
- If start date is after Baseline, it is a concomitant medication regardless.

Prior and concomitant medications will be summarized separately by WHO ATC class and preferred name. These summaries will present the number and percentage of subjects using each medication. Subjects may have more than 1 medication per ATC class and preferred name. At each level of subject summarization, a subject is counted once if he/she reported 1 or more medications at that level. Each summary will be ordered alphabetically by ATC by descending PT subject count within each ATC.

Prior AD Medications

All systemic (oral and injectable) medications used by the subject for treatment of AD prior to 30 days before the Screening visit will be collected. Prior AD medications will be summarized by frequency count and percent by treatment and overall.

10. EFFICACY ANALYSES

All efficacy analyses will be based on the ITT population and will be repeated for the PP population for the primary and secondary efficacy endpoints as supportive analyses.

10.1 Efficacy Variables

[figure not shown]
The primary efficacy endpoint is proportion of subjects who achieve vIGA-ADTM score of clear (0) or almost clear (1) and at least a 2-grade reduction from Baseline at Week 8.

Secondary efficacy endpoints include the following:

- Proportion of subjects with $\geq 75\%$ improvement in EASI score from Baseline at Week 8
- Mean change in %BSA affected from Baseline at Week 8
- Proportion of subjects with ≥90% improvement in EASI score from Baseline to Week 8
- Proportion of subjects ≥12 years old with a Baseline PP-NRS score ≥4 who achieve ≥4-point reduction in the average weekly PP-NRS from Baseline at Week 8

Exploratory efficacy endpoints include the following:

[figure not shown]

